6.5 Other Variables

- FLT3-ITD mutation status
- FLT3-TKD mutation status
- FLT3 mutation status

Either of FLT3-ITD mutation status or FLT3-TKD mutation status is positive, this variable shows positive.

- MRD

MRD negative is defined as summed FLT3-ITD signal ratio of any post-baseline sample $\leq 10^{-4}$. MRD positive is defined as summed FLT3-ITD signal ratio of any post-baseline sample $> 10^{-4}$.

- MR
MR is defined as summed FLT3-ITD signal ratio of any post-baseline sample $\leq 10^{-2}$.
No MR is defined as summed FLT3-ITD signal ratio of any post-baseline sample $> 10^{-2}$.
- FLT3-ITD signal ratio
FLT3-ITD signal ratio is defined as the ratio of FLT3-ITD sequence reads divided by the total number of FLT3 sequence reads. This is being calculated by central laboratory. For subjects with more than one FLT3-ITD variant, the FLT3-ITD signal ratio will be summed at each timepoint.
- Duration of exposure (days)
Duration of exposure to each treatment will be calculated in days, using the following formula:
 - Duration of exposure for each treatment cycle is defined as Last dose date – First dose date + 1 – (on-study HSCT period for subjects undergo on-study HSCT) for each cycle. For Phase1 part, last dose date of study drug exposure = (initial dose date of the cycle + 14 – 1) if last dose date of the cycle is not captured on dosing CRF.
 - Duration of exposure for each treatment period is calculated as sum of the duration of exposure for each treatment cycle.
 - Duration of exposure during study for study drug =
(Duration of exposure for Induction period) + (Duration of exposure for Consolidation period) + (Duration of exposure for Maintenance period).When the last date of exposure is beyond cutoff date, the cutoff date will be used as the last date of exposure. When the start or stop date is missing, then the exposure will be treated as missing.
- Number of dosing days (days)
Defined as number of days with non-zero dosing.
Number of dosing days is calculated for each treatment period.
- Cumulative dose (mg or g)
Defined as total amount of drug given to a patient, which calculated as follows:
 - ASP2215: Sum of (actual dose level * number of dosing days within each dose level)
 - Chemotherapy: Sum of actual dose across the days when administered.
Actual dose is calculated as:
(Actual volume administered / Total volume prepared)* Intended dose * Body surface area.

If number of doses taken is unknown, it will be treated as missing.

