7.11.5 Visit Windows

[Phase 1 part]

Visit windows are allowed for certain visits per the schedule of assessments. Subject data will not be excluded from analyses due to the subject’s failure to comply with the visit schedule. In the case of multiple observations at a specific visit, the observation which is closest to the target date will be used. If the observations have the same distance to the target visit, the latest one will be used. The baseline visit is the last measurement taken prior to initial treatment.

- Visit Windows for Laboratory Tests

Induction period			
Assessment timing	Scheduled date (Day 1: Day 1 of each cycle Start of treatment)	Acceptable time range	Remarks
Screening	—	7 days before dosing – 1 day before dosing (Before dosing if the screening and Day 1 of Cycle 1 overlap).	Treatment on Day 1 may be started on the day informed consent is obtained when the investigator or subinvestigator judges that immediate treatment is required due to rapid proliferative disease progression. In this case, among the test items specified in both screening and Day 1 of Cycle 1 are not required to be performed twice.
Day 1	Day 1	Before dosing on the scheduled date	Same as above
Day 4	Day 4	Scheduled date	
Day 8	Day 8	Scheduled date	
Day 15	Day 15	Scheduled date ± 1 day	
Day 28	Day 28	Scheduled date ± 7 days	
Day 42	Day 42	Scheduled date + 14 days	
Consolidation period			
Assessment timing	Scheduled date (Day 1: Day 1 of each cycle Start of treatment)	Acceptable time range	Remarks
Day 1	Day 1	Scheduled date	
Day 4	Day 4	Scheduled date	
Day 8	Day 8	Scheduled date	
Day 15	Day 15	Scheduled date – 1 day	
Day 28	Day 28	Scheduled date ± 7 days	
Maintenance period			
Assessment timing	Scheduled date (Day 1: Cycle 1 Day 1 Start of treatment)	Acceptable time range	Remarks
Cycle 1 Day 1	Day 1	Scheduled date	
Cycle X Day 1	Day 28 (X – 1) + 1	Scheduled date ± 3 days	X = Cycle 2 and subsequent cycles

End of treatment (for any period) or at the end of Cycle 26 of the maintenance period	Date of judgment of discontinuation or Cycle 26 Day 28 of the maintenance period	Scheduled date + 7 days	If the scheduled tests at discontinuation have been performed after the final study drug administration, the tests do not have to be repeated even if they were performed before the date of judgment of discontinuation.
---	--	----------------------------	---

● Visit Windows for Vital Signs

Induction period			

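### Exposure duration: the Phase 1 14-day fill also covers 28-day maintenance cycles and conflicts with the missing-date rule, and the HSCT subtraction is right only if the transplant interval lies inside a cycle

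*SAP*

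**What the plan says.** All the rules stand in SAP section 6.5, under duration of exposure.

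- Cycle level: the last dose date less the first dose date, plus 1, less the "on-study HSCT period for subjects undergo on-study HSCT) for each cycle".
- Period level: "Duration of exposure for each treatment period is calculated as sum of the duration of exposure for each treatment cycle".
- Study level, for the study drug: "Duration of exposure for Induction period) + (Duration of exposure for Consolidation period) + (Duration of exposure for Maintenance period". Maintenance is therefore included.
- Phase 1 fill: the last dose date becomes "initial dose date of the cycle + 14 – 1) if last dose date of the cycle is not captured on dosing CRF". No treatment period is named.
- Closing rule of the same item: "When the start or stop date is missing, then the exposure will be treated as missing".

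Section 7.11.5 shows the length of a Phase 1 maintenance cycle. The end-of-maintenance visit is set at "Cycle 26 Day 28 of the maintenance period", and each later cycle starts on day 28(X − 1) + 1.

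Section 6.5 then divides cumulative dose by this duration to get dose intensity, and divides that by a planned 120 mg per day for ASP2215 to get relative dose intensity. Both are reported per treatment period. Section 7.3.1 also groups exposure time into categories with cut points at 14, 42, 84 and 168 days.

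**The concern.** Three features of this item can distort the result.

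1. The 14-day fill appears to come from the induction and consolidation dosing pattern, but its wording reaches every Phase 1 cycle. In maintenance it can cut a cycle to half its length.
2. The fill and the closing missing-date sentence both apply to a Phase 1 cycle without a captured last dose date. One returns 14 days and the other returns missing, and no order between them is given.
3. The HSCT deduction is made inside the cycle formula, and periods are sums of cycles. A transplant interval between two cycles lies in no cycle's first-to-last-dose span, so deducting it takes off days that were never added.

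Exposure that is too short inflates dose intensity and relative dose intensity and can move a subject to a lower exposure category. Safety and tolerability of maintenance is a Phase 1 primary objective, and safety of the regimen including maintenance is a Phase 2 secondary objective (sections 3.1.1 and 3.1.2). These figures are the background against which that safety is read.

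**Working it through.** **Where the 14 days come from.** Three places in the SAP agree with 14 dosing days outside maintenance.

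- Induction pre-dose ECG and PK visits run from Day 4 to Day 17 (section 7.11.5): 17 − 4 + 1 = 14.
- In consolidation, Day 1 has a pre-dose sample, and the Day 15 sample must be taken pre-dose only if it is moved to Day 14. That points to dosing on Days 1 to 14: 14 − 1 + 1 = 14.
- The DLT evaluability example (sections 3.2 and 5.3) links less than 80% of the dose to three or more missed daily doses. With 14 doses, 3 missed gives 11/14 = 78.6% and 2 missed gives 12/14 = 85.7%, which fits. With 28 doses, 3 missed gives 25/28 = 89.3%, which does not.

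**Fill applied to maintenance.** Assume daily dosing through a full 28-day cycle; the planned 120 mg per day, applied to all periods, implies this but the SAP does not state it. Filled length = 14, true length = 28. If only the last of k maintenance cycles lacks a stop date, the period counts 28(k − 1) + 14 days. If the dosing days are nevertheless fully known, relative dose intensity = 28k / [28(k − 1) + 14].

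| Cycles k | True days | Counted days | Relative dose intensity |
|---|---|---|---|
| 1 | 28 | 14 | 200% |
| 6 | 168 | 154 | 109.1% |
| 26 | 728 | 714 | 102.0% |

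If dosing days are counted only up to the filled date, relative dose intensity stays at 100%. If the number of doses is unknown, section 6.5 makes cumulative dose missing, and relative dose intensity with it.

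**HSCT term.** Let G be the HSCT interval in days, here an assumption. Take it to be the days without ASP2215 between the last dose before and the first dose after transplant.

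- Interval inside one cycle: that cycle's first-to-last span is 28 + G, and (28 + G) − G = 28. The formula is right.
- Interval between cycles, deducted once, six maintenance cycles: counted days = 168 − G, and relative dose intensity at full dosing = 168/(168 − G).

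| Assumed G | Counted days (true 168) | Relative dose intensity (true 100%) |
|---|---|---|
| 30 | 138 | 121.7% |
| 60 | 108 | 155.6% |
| 90 | 78 | 215.4% |
| 120 | 48 | 350.0% |

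Exposure category: assume three earlier cycles of 14 dosing days (42 days) as well. True total is 42 + 168 = 210 days. With a 60-day gap deducted once it is 210 − 60 = 150 days, which moves the subject from the top category (168 days and above) to the one below.

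**The case against.** The strongest defence concerns the HSCT term. The SAP does not say whether an on-study transplant falls between cycles or interrupts one that later resumes. In the second case the deduction is needed and correct. The phrase about each cycle can also be read as that cycle's own HSCT days, which is zero where there are none. How cycles are numbered around HSCT may be settled in the protocol, which is not at hand. This stands: the fault is an open wording, not a proven error.

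A reader might go further and infer that the same interval comes off every cycle. Six 28-day cycles with a 60-day gap would then give 6 × (28 − 60) = −192 days. The text does not require this. It would mean deducting the transplant even from cycles in which no transplant occurred.

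On the fill, it can be said that it touches only Phase 1 (target 6 subjects) and only cycles whose last dose date is not on the dosing CRF, and that nothing shows that any maintenance cycle lacks one. It can also be said that a filled date is no longer missing, so the closing sentence still governs missing start dates and Phase 2. Both points limit the size. But the SAP neither restricts the fill to certain periods nor states that precedence.

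A reader might also infer from the 200% figure that dose intensity will generally be wrong. That figure needs a maintenance period of exactly one cycle, with all 28 dosing days known although the last dose date is not. In other situations the distortion is small, absent, or the value is missing.

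**Conclusion.** The point holds, as a minor one. Two parts follow from the text itself: the Phase 1 fill is not limited to the periods it fits, so a fully dosed 28-day maintenance cycle without a captured stop date would count as 14 days; and the fill and the missing-date sentence give two answers for the same record. The first rests on daily dosing throughout the maintenance cycle.

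The HSCT part is conditional. It misstates exposure only if the interval lies between cycles and is deducted anyway. The sizes shown (108 instead of 168 days and 156% for an assumed 60-day gap) depend on that condition, on the assumed gap and on six fully dosed maintenance cycles. The documents do not support a flat statement that exposure and dose intensity come out wrong.

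Only descriptive summaries of exposure, dose intensity and relative dose intensity are affected. The primary CR analysis does not use them.

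**What to change.** Change four things in the duration-of-exposure item of section 6.5:

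1. Limit the + 14 − 1 fill to Phase 1 induction and consolidation cycles.
2. For maintenance cycles without a captured last dose date, use the last dosing record available for that cycle, or treat exposure as missing. Name which.
3. State that the missing-date sentence applies only where the fill does not.
4. Reword the HSCT term so that only HSCT days lying between that cycle's first and last dose dates are subtracted, and zero if there are none.

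The fourth change gives the right length whether the interval falls inside a cycle or between cycles, and alters nothing if this was already the intention. The cost is a few sentences of SAP text and a small change to the exposure program. No new data are needed.

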7 STATISTICAL METHODOLOGY

7.1 General Considerations

- For continuous variables, descriptive statistics will include the number of subjects (n), mean, standard deviation, minimum, Q1, median, Q3 and maximum. When needed, the use of other percentiles (e.g. 10% and 90%) will be mentioned in the relevant Section.
- For continuous PK parameters, the coefficient of variation will be calculated, and for C_{max} and AUCs, the geometric mean will also be calculated. GM will not be calculated if at least one value is the BLQ.
- t_{max} will be summarized using median and range.
- Frequencies and percentages will be displayed for categorical data.
- Percentages by categories will be based on the number of subjects with no missing data, i.e. will add up to 100%.
- All data processing, summarization, and analyses will be performed using SAS (ver. 9.4) or higher on Red Hat Enterprise Linux.
- Specifications for Table, Figures, and data listing formats can be found in the TLF specifications for this study.
- MedDRA (version 23.0) will be used as the coding dictionary for adverse event and medical history.
- WHODD(B2) (V2016Sep) for Phase 1 part and WHODD(B3) (V2018Mar) for Phase 2 part will be used as the coding dictionary for previous and concomitant medications.
- The assessments impacted by COVID-19 will be listed and sensitivity analyses to assess the impact of COVID-19 for some efficacy may be performed if needed.
- [Phase 1 part] All analysis will be presented by the dose-evaluation part, expansion part and overall, unless specifically stated otherwise.
- [Phase 1 part] The data of a subject who was allocated to ASP2215 40 mg per day will be used only for listings.

7.2 Study Population

7.2.1 Disposition of Subjects

[Phase 1 part]

The following subject data will be presented:

- Number and percentage of subjects with informed consent, discontinued before allocation to the treatment, allocated to the treatment (overall only).
- Number and percentage of subjects who were included/excluded in each analysis set.
- Number and percentage of subjects excluded from each analysis set by reason.
- Number and percentage of subjects completed and discontinued the study, by primary reason for study discontinuation for subjects allocated to the treatment.
- Number and percentage of subjects completed and discontinued the post-study, by primary reason for post-study discontinuation for subjects allocated to the treatment.

[Phase 2 part]

- Number and percentage of subjects with informed consent, discontinued before pre-registration to the study, allocation to the treatment, discontinued before registration to the study and allocation to study drug.
- Number and percentage of subjects completed and discontinued the pre-registration period, by primary pre-registration status.
- Number and percentage of subjects completed and discontinued the registration period, by primary registration status.
- Number and percentage of subjects who were included/excluded in each analysis set.
- Number and percentage of subjects excluded from each analysis set by reason.
- Number and percentage of subjects completed and discontinued the study, by primary reason for study discontinuation for subjects allocated to the treatment.
- Number and percentage of subjects completed and discontinued the follow-up, by primary reason for follow-up discontinuation for subjects allocated to the treatment.
- Number and percentage of subjects completed and discontinued the long-term follow-up, by primary reason for long-term follow-up discontinuation for subjects allocated to the treatment.

7.2.2 Protocol Deviations

[Phase 1 part]

Not applicable.

[Phase 2 part]

Protocol deviations as defined in the study protocol (Section 10.3 Major Protocol Deviations) will be assessed for all subjects who received treatment. The number and percentage of subjects meeting any criteria will be summarized for each criterion and overall, by study site. Subjects deviating from a criterion more than once will be counted once for the corresponding criterion. Any subjects who have more than one protocol deviation will be counted once in the overall summary. A data listing will be provided by site and subject.

The protocol deviation criteria will be uniquely identified in the summary table and listing. The unique identifiers will be as follows:

PD1 - Entered into the study even though they did not satisfy entry criteria,

PD2 - Developed withdrawal criteria during the study and was not withdrawn,

PD3 - Received wrong treatment or incorrect dose,

PD4 - Received excluded concomitant treatment.

7.2.3 Demographic and Other Baseline Characteristics

[Phase 1 part]

Analysis set: SAF, FAS, DDAS, PKAS, PDAS

Demographic and other baseline characteristics will be summarized by descriptive statistics or categorical analysis.

The following demographic variables will be summarized and presented.

Table 1.1. Demographic Variables and Analysis Methods for all analysis sets

Item	Classification	Analysis Methods
Age (years)	Measurement value <65 years, >=65 years	Descriptive statistics Categorical analysis
Height [Screening](cm)	Measurement value	Descriptive statistics
Weight (kg)	Measurement value	Descriptive statistics
BMI (kg/m ²)	$BMI (kg/m^2) = Weight (kg) / (Height (cm) / 100)^2$	Descriptive statistics
BSA (m ²)	$BSA (m^2) = Weight (kg) ^ 0.425 x Height (cm) ^ 0.725 x 0.007184$	Descriptive statistics
Subject ECOG Status	0, 1, 2, 3, 4	Categorical analysis
Sex	Male, Female, Unknown	Categorical analysis
Race	White, Black or African American, Asian, American Indian or Alaska Native, Native Hawaiian or Other Pacific Islander, Other	Categorical analysis

BMI: Body Mass Index, BSA: Body Surface Area, ECOG: Eastern Cooperative Oncology Group

[Phase 2 part]

Analysis set: SAF, FAS, PKAS, MAS

Demographic and other baseline characteristics will be summarized by descriptive statistics or categorical analysis.

The following demographic variables will be summarized and presented.

Table 1.2. Demographic Variables and Analysis Methods for all analysis sets

Item	Classification	Analysis Methods
Age (years)	Measurement value <65 years, >=65 years	Descriptive statistics Categorical analysis
Height [Screening](cm)	Measurement value	Descriptive statistics
Weight [Screening] (kg)	Measurement value	Descriptive statistics
BMI (kg/m ²)	$BMI (kg/m^2) = Weight (kg) / (Height (cm) / 100)^2$	Descriptive statistics
BSA (m ²)	$BSA (m^2) = Weight (kg) ^ 0.425 \times Height (cm) ^ 0.725 \times 0.007184$	Descriptive statistics
Subject ECOG Status	0, 1, 2, 3, 4	Categorical analysis
Sex	Male, Female, Unknown	Categorical analysis
Race	White, Black or African American, American Indian or Alaska Native, Asian Indian, Chinese, Filipino, Japanese, Korean, Taiwanese, Vietnamese, Other Asian, Native Hawaiian, Guamanian or Chamorro, Samoan and Other Pacific Islander	Categorical analysis
Region	Japan, Korea, Taiwan	Categorical analysis

BMI: Body Mass Index, BSA: Body Surface Area, ECOG: Eastern Cooperative Oncology Group

Analysis set: SAF

Frequency tabulations for AML disease history including AML subtype as classified by WHO classification and FAB classification, risk status with specific cytogenetic patterns, antecedent hematological disorder (Phase 1 part only), central nervous system leukemia (Phase 1 part only), FLT3-ITD mutation status (Phase 1 part only), FLT3 point mutation status (Phase 1 part only) will be presented.

Medical history other than AML will be coded in MedDRA and summarized by SOC and PT as well as by PT alone. Baseline conditions are defined as those ongoing at the time of informed consent or arise following the time of informed consent and before the first dose of the treatment. For ongoing medical conditions, CTCAE grade will be provided in listing.

Result from MUGA scan or ECHO, if performed, will be provided in listing.

7.2.4 Previous and Concomitant Medications

Analysis set: SAF

Previous medications are coded with WHODD and will be summarized by therapeutic subgroup (ATC 2nd level) and chemical subgroup (ATC 4th level) and preferred WHO name.

As with previous medication, concomitant medication will be summarized by therapeutic subgroup (ATC 2nd level) and chemical subgroup (ATC 4th level) and preferred WHO name. Subjects taking the same medication multiple times will be counted once per medication and investigational period. A medication which can be classified into several chemical and/or therapeutic subgroups is presented in all chemical and therapeutic subgroups.

Concomitant medication will also be summarized by preferred WHO name, and presented in decreasing order of frequency based on the total number of subjects took each medication.

7.2.5 Previous and Concomitant Transfusions

Analysis set: SAF

Frequency tabulations of subjects received transfusions and blood product will be presented for previous transfusion and concomitant transfusion. Descriptive statistics will be presented for number of transfusion unit received per subject for each type of blood product.

7.2.6 Non-Medication Therapy

Analysis set: SAF

Frequency tabulations of subjects with non-medication therapy and reason for use will be presented. Number of non-medication therapy received per subject will be summarized using descriptive statistics.

7.3 Study Drugs

7.3.1 Exposure

Analysis set: SAF

The following information on ASP2215 exposure will be presented:

- Descriptive statistics for cumulative dose of the treatment subject was exposed to, number of dosing days, average of daily dose, dose intensity, and relative dose intensity; and
- Number and percent of subject with dose reduction and interruption.

Duration of exposure will be summarized in two ways:

- Descriptive statistics will be presented.
- Exposure time will be categorized according to the following categories (study drug only):
 - less than 14 days
 - at least 14 days, less than 42 days
 - at least 42 days, less than 84 days
 - at least 84 days, less than 168 days
 - 168 days or more
 - Unknown.

Number and percentage of subjects in each of these categories will be summarized.

Listing of subjects with dose reduction and interruption will also be provided.

7.4 Analysis of Efficacy

[Phase 1 part]

The efficacy analysis will be performed on the FAS.

For response variables, best response after each treatment therapy period will be summarized. The number and percentage of subjects in each category will be presented together with two-sided exact 95% CIs based on binomial distribution. Swimmer's plot will be presented for response variables.

For time-to-event variables efficacy analysis will be summarized using descriptive statistics. The survival curve and the median will be estimated using the Kaplan-Meier method and will be reported along with the corresponding 95% CIs.

[Phase 2 part]

The efficacy analysis will be performed on the FAS and TTE-FAS. The interpretation of statistical results will be based on the FAS. The TTE-FAS will be used to analyze OS and EFS. Analysis of MRD and MR will be performed using MAS.

Primary efficacy variable

For primary efficacy variable, CR rate after induction therapy period, the two-sided 90% exact CI by Clopper-Pearson method will be calculated. The lower limit will be used to compare with the benchmark of CR rate of 55%. The number and percentage of subjects in each category and swimmer's plot will also be presented. As a supportive analysis, CR rate after induction therapy period reported by Day 60 and CR rate after induction therapy period not being dependent on RBC and platelet transfusion (No Transfusion of RBC and Platelet within 1 week prior to disease assessment) will also be calculated.

Other efficacy variables

For other efficacy variables, analysis method will be described as follows:

Categorical variables:

The number and percentage of subjects in each category will be presented together with two-sided exact 95% CIs based on binomial distribution. Swimmer's plot will be presented for response variables.

For response assessment variables, best response rate after each treatment therapy will be summarized. The number and percentage of subjects in each category will be presented together with two-sided exact 95% CIs based on binomial distribution. For subjects who undergo HSCT, any response assessment data after HSCT will not be used (i.e. for those subjects, only response assessment data before HSCT will be used).

As a sensitivity analysis, response assessment will be defined similarly as the above analysis, however, all response assessment data will be used even if there were subjects who undergo HSCT (i.e. response assessment data after HSCT will also be used).

Time-to-event variables:

For time-to-event variables efficacy analysis will be summarized using descriptive statistics. The survival curve and the median will be estimated using the Kaplan-Meier method and will be reported along with the corresponding 95% CIs. Kaplan-Meier plot will be presented.

